### **Self-Report Assessments:**

*Characteristics of Respondents (CORE):* The following data will be collected via the CORE: demographics (age, gender, race, employment status, and highest level of education completed), diagnosis, neurological level of injury, time since onset of injury, general health status, secondary health conditions, medications, and mobility device used.

*PROMIS Measures:* The PROMIS measures will be used to assess six different domains: emotional distress, emotional support, sleep, pain interference, pain intensity, and fatigue. Individuals respond to the items in each domain using a five-point Likert scale. The six domains are scored individually.

*Leisure Time Physical Activity Questionnaire for People with SCI (LTPAQ-SCI):* The LTPAQ-SCI is a self-report measure of leisure time physical activity that assesses minutes of mild, moderate, and heavy intensity activity over the previous seven days. The survey will be collected during screening to determine eligibility.

*The SCI Exercise Self-Efficacy Scale (ESES):* The ESES is a 10-item, SCI-

---

specific scale developed to measure perceived exercise self-efficacy for various types of physical activities. The scale requires individuals to self-report their confidence in performing physical activities and exercise. One dichotomous item asks whether the individual has exercised at home and/or in a gym in the past 12 months. Individuals respond to the 10 items using a four-point Likert scale (1: not at all true, 4: always true); the total score is then derived by summing the scores for the individual items; scores range from 10 to 40. Higher scores indicate greater perceived self-efficacy. The dichotomous item is used to estimate the participant's average exercise activity.

**Community Participation Index (CPI):** The CPI is a valid and reliable assessment of involvement in life situations and individual control over participation. For each item, respondents rate frequency (either in days, hours, or times per week, depending on the activity), whether it was important (yes/no), and to what extent they do the item (too much, enough, or not enough). The measure is used as a categorical variable using validated scores. Participation will be assessed at baseline and both follow-up assessments to determine the level of change in participation for each MWU with SCI.

**RM 4-FM: Motivation for Physical Activity and Exercise/Working Out:** This questionnaire is designed to assess whether the participants are extrinsically or intrinsically motivated to engage in a physical activity. The questionnaire makes a statement of "I try, or would like to try, to be physical active regularly," and participants must rate themselves on a Likert scale between 1 (not true at all), to 7 (very true).

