## **2.d Randomization Method and Blinding**

Randomization does not occur until after the initial assessment is completed. Immediately following completion of the initial assessment, each participant will be randomly assigned to either the CBEI ( $n = 20$ ) or EEG ( $n = 20$ ). To control for selection bias, stratified randomization will be used to ensure that the CBEI and EEG are balanced with respect to how long the participant has been injured ( $<2$  years or  $\geq 2$  years), the participant's level of injury (below C7 or C7 and above), age ( $<40$  years or  $\geq 40$  years of age), and gender. This will control for a large imbalance of participants allocated to one intervention. Research staff performing the assessments will be blinded to group randomization.

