## **G Statistical Plan**

### **G1 Sample Size Determination and Power**

This is a pilot study, with our primary interests in outcome variability and co-variability and estimates of feasibility and acceptability, which will aid in the planning of a larger trial. The sample size of 40 participants was selected to provide enough participants to assess the research protocol, determine trends in change, and provide data to calculate sample sizes for a larger RCT.

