### **G4 Statistical Methods**

*Aim 1:* Data will be collected and managed using Research Electronic Data Capture (REDCap) and exported to SPSS for analysis. Descriptive statistics will be used to describe the CBEI and the EEG. The data will be examined for normality, outliers, and errors. To examine whether the datasets meet the assumptions of normality, a Shapiro-Wilks test will be conducted. The assumptions of homogeneity of variance and homogeneity of covariance will be examined with Box's M and Mauchly's W tests, respectively. To examine the presence of outliers, histograms will be used. The purpose of the analysis is to compare the post VO2peak measures (primary outcome) between the two groups. First, a two sample t test (or non-parametric Wilcoxon test) will be used for unadjusted analyses. Then we will use a linear regression to compare VO2peak between the CBEI and EEG, adjusting for pre-VO2peak measures and other potential covariates. For other outcomes, based on the measurement scale, a similar analysis approach (unadjusted and adjusted) will be used. For binary outcomes, a Pearson Chi-square or fisher exact test will be used for unadjusted analyses, and a logistic regression model will be used for adjusted analyses. For continuous outcomes, we will perform

---

analyses similar to those of the VO2peak outcome. Additionally, effect size (d) associated with the intervention will be calculated using Cohen's *d* and will be interpreted as small (*d* ≤ .2), moderate (*d* ~ .5), or large (*d* ≥ .8). We will explore whether results differ depending on level of SCI and length of time living with an SCI. We will use dummy variables for these two variables and test the interaction term (intervention-by-the-dummy) in the model.

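### The Community Participation Index (CPI) is to be used as a categorical variable, with no categories or change rule given, although it is meant to measure each person's change; analysing its scores on their own scale would be more precise.

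*Combined protocol and SAP*

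**What the plan says.** F3, Self-Report Assessments, describes the CPI items: "respondents rate frequency (either in days, hours, or times per week, depending on the activity), whether it was important (yes/no"), and a three-level rating of whether the person does the activity too much, enough or not enough. It then states "The measure is used as a categorical variable using validated scores". The next sentence has participation assessed at baseline and both follow-ups "to determine the level of change in participation for each MWU with SCI".

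Neither that section nor G4 gives the number of categories, where they are cut, or how movement between them becomes a level of change.

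G4 sets the general rule for outcomes other than VO2peak: "For other outcomes, based on the measurement scale, a similar analysis approach (unadjusted and adjusted) will be used". It then spells this out for two kinds of outcome. Where an outcome has two levels, the planned methods are a chi-square or Fisher test without adjustment and logistic regression with it. Where an outcome is continuous, G4 repeats the VO2peak approach: a two-sample t test or Wilcoxon test, then linear regression adjusted for the baseline value. No other scale type is covered.

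G1 explains the size of the trial: "The sample size of 40 participants was selected to provide enough participants to assess the research protocol, determine trends in change", and to supply data for sizing a larger trial. It gives no power calculation for any outcome.

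The CPI does not appear in the primary hypothesis (A2), the primary aim (C1), or the primary and secondary outcome variables listed in C3.

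**The concern.** The two CPI sentences pull against each other. A categorical variable records change only when someone crosses a boundary. A person who improves within a category is recorded as unchanged, and one who starts in the top category cannot be seen to improve.

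The analysis is also unsettled. If the CPI has two categories, G4 sends it to chi-square or Fisher and logistic regression with 20 per arm. If it has three or more, G4 names nothing. Choosing the number of categories after the data are in would leave a choice that can affect the result.

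What is at stake is precision. With 40 people, estimates of participation change are already imprecise, and the pilot is meant to show trends in change and how much outcomes vary. If a usable score exists, analysing categories instead gives away information at no benefit.

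**Working it through.** The plan states no power, alpha, SD or effect for the CPI, so there is no figure to reproduce. The check shows how much information categorising costs for different numbers of categories.

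**Inputs from the documents**
- 20 per arm (E1 and 2.d).
- d = 0.5 and 0.8, the moderate and large bands G4 uses to interpret Cohen's d. They are not assumed CPI effects.
- Both unadjusted and adjusted analyses (G4).

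**Assumptions**
- A normal underlying score, k equal-sized categories, two-sided alpha 0.05.
- Pre-post correlation r of 0.5 or 0.7.
- No dropout.

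**Step 1: individual change.** Let everyone's score rise by s SD. A person crosses a cut c if the baseline lies between c − s and c.
- Two categories (cut at 0), s = 0.5: Φ(0) − Φ(−0.5) = 0.500 − 0.309 = 0.191. So 81% cross nothing.
- Three categories (cuts at ±0.431), s = 0.5: [Φ(−0.431) − Φ(−0.931)] + [Φ(0.431) − Φ(−0.069)] = 0.157 + 0.194 = 0.352 before rounding of the parts. So 65% cross nothing.

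Share of true shifts that cross no boundary:

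| Shift | k = 2 | k = 3 | k = 4 | k = 5 |
|---|---|---|---|---|
| 0.5 SD | 81% | 65% | 50% | 35% |
| 0.8 SD | 71% | 47% | 32% | 25% |

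**Step 2: unadjusted power for a median split.**
- Score, normal approximation: Φ(d√(20/2) − 1.96). At d = 0.5: Φ(1.581 − 1.96) = 0.352. At d = 0.8: Φ(2.530 − 1.96) = 0.716.
- Median split: the proportions above the cut are Φ(d/2) and 1 − Φ(d/2). At d = 0.5 these are 0.599 and 0.401; at d = 0.8, 0.655 and 0.345. Power is Φ([p1 − p0 − 1.96√(2 × 0.25/20)] / √([p1(1 − p1) + p0(1 − p0)]/20)), which gives 0.234 and 0.50.
- Relative loss: 1 − 0.234/0.352 = 34%, and 1 − 0.50/0.716 = 30%.
- Fisher's exact test against the exact t test gives 0.140 against 0.338 and 0.363 against 0.693, losses of 59% and 48%.

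**Step 3: baseline-adjusted power.** Simulation, 3,000 trials per setting. The follow-up value is regressed on arm and baseline value. Both values are scores, or both are categories scored in order. Losses come from unrounded results and can differ by a point from the figures shown.

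| d, r | k = 2: score → category (loss) | k = 3 | k = 5 |
|---|---|---|---|
| 0.5, 0.5 | 0.414 → 0.259 (37%) | 0.433 → 0.343 (21%) | 0.434 → 0.384 (12%) |
| 0.5, 0.7 | 0.592 → 0.299 (50%) | 0.565 → 0.386 (32%) | 0.576 → 0.483 (16%) |
| 0.8, 0.5 | 0.796 → 0.540 (32%) | 0.795 → 0.655 (18%) | 0.798 → 0.728 (9%) |
| 0.8, 0.7 | 0.918 → 0.614 (33%) | 0.931 → 0.749 (19%) | 0.922 → 0.861 (7%) |

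Four categories lose 11-25%. The unadjusted loss in the same simulation is 13-14% for three categories, 8-15% for four and 6-9% for five.

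For k = 2, a separate simulation (1,500 trials per setting) used logistic regression, as G4 would. It gave 25-31% power against 40-57% on the score at d = 0.5, and 54-59% against 79-92% at d = 0.8. Losses run from 1 − 54/79 = 32% to 1 − 31/57 = 46%.

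**The case against.** A reader might infer that most real changes in participation will go unregistered and that power will fall by about a third. The documents do not support that as a statement of fact, because nowhere do they say that the CPI is split in two. With three categories and a 0.8 SD shift, 53% of people do cross a cut. With five ordered categories the adjusted loss is 7-16%. The larger figures belong to a near-median two-way split. This objection stands in full, and the size must be given by number of categories.

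It may also be said that the wording describes the instrument's established scoring and not a decision to cut a continuous total. Two of the three responses per item are categorical, and the scoring is in cited sources that the documents do not reproduce. This stands as an uncertainty: whether a continuous total exists cannot be confirmed, so the fix needs a fallback. It does not remove the gap, because ordered categories also need stated levels, a change rule and a method.

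A reader might further infer that the SD and pre-post correlation of participation are lost to the larger trial. They are not, if the scores are held: both can be computed whatever form the group comparison takes. Nor do the documents say that participation will be used to size that trial.

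Finally, the CPI is not a listed outcome, the trial is not sized by power, and the CPI text announces no between-arm test. All true, and this limits the consequence. G4's rule for other outcomes would still reach the CPI if the arms are compared on it, and the stated purpose of individual change is affected in any case.

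**Conclusion.** The point holds in a limited form. The plan makes the CPI categorical without giving categories, cut points or a change rule, although its purpose is each person's change, and G4 has no method for more than two categories.

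The cost runs from severe to small: about 32-50% of baseline-adjusted power for a near-median split, 18-32% for three ordered categories, 11-25% for four and 7-16% for five. The share of true 0.5 SD shifts left unregistered falls from 81% to 35% over the same range. Apart from the 20 per arm and the two effect bands, the inputs are assumptions: normality, equal-sized categories, alpha, correlation and full retention. Unequal categories or dropout would change the figures.

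Nothing here touches VO2peak, which G4 names as the primary outcome, or the trial's main conclusion. The loss is in the precision of the participation estimates and in the ability to see individual change. It is worth correcting because the correction is nearly free.

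**What to change.** Replace the CPI sentence in F3 so that the validated scores are analysed on their own scale with G4's baseline-adjusted linear regression: T2 score on arm and T1 score, and likewise T3 score on arm and T1 score. Report the mean difference with its confidence interval, the SD and the pre-post correlation, and report individual change as the difference in score. Use categories for description only.

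If the validated scoring yields only ordered categories, list them all, state how change is derived, and prespecify in G4 an ordinal model adjusted for the baseline category. Do not dichotomise.

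The cost is a change of wording in F3 and a line in G4. No new data are needed, since the plan already refers to validated scores. The one preliminary step is to confirm from the instrument's scoring instructions which kind of score it produces.

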#### ***Physical Assessments:***

**VO2peak:** Measured using a standard computer-integrated, open-circuit, breath-by-breath metabolic measurement system (TrueOne 2400, Parvo Medics, Sandy, UT, US) while the participant performs a graded-exercise test on an arm crank ergometer (ACE), (SCIFIT PRO2, Life Fitness, Tulsa, OK, US). In addition, an H7 Heart Rate Sensor (Polar Electro Inc., Lake Success, NY, US) will be placed on each participant to monitor heart rate during testing. Each participant will be fitted with a silicone mask to cover his or her mouth and nose while performing the exercise test, which is typically completed in 8–12 minutes depending on the participant's fitness level. The protocol involves a 3-minute warm-up at a workload of 8–10 watts (W) followed by a standard ACE ramp protocol. The ramp protocol requires participants to maintain 60 revolutions per minute (rpm) with incremental increases by 7 W every minute, until exhaustion.

**Muscle Strength:** The participants' muscle strength will be tested using Equalizer accessible exercise equipment to establish their one-repetition maximum (1-RM) on four upper-body exercises tested on each arm (left and right arm bicep curls, left and right arm chest press, left and right arm rowing, and left and right arm rickshaw triceps extension). Each exercise represents a different motion (pushing or pulling) in varying planes. For example, the rickshaw exercise involves pushing downward on straps connected to weights. Upon completion of one repetition during the strength assessment, the participants will report their arm movements as *easy*, *moderate*, or *hard*. The greatest amount of weight lifted for the complete range of motion for the lift will be recorded as the 1-RM. This will be used in determining the exercise routine for participants enrolled in the exercise intervention.

**The 6-minute Push Test (6MPT):** The 6MPT is a functional mobility and physical fitness test involving MWUs propelling a designated 30-meter loop. Participants are

---

asked to propel as far as possible on the course within 6 minutes. Total distance propelled is determined by tallying the number of completed 30-meter loops and measuring the partially completed final lap using a tape measure.

**Anthropometrics and Vitals:** Body mass will be measured by height, weight (using a wheelchair accessible scale), and BMI. Resting and post-testing blood pressure and heart rate will also be taken at each testing session.

**Qualitative Data:** After completion of the 12-week sessions, participants will complete a 60-minute, semi-structured interview. Interviews will be conducted by applying general rules for qualitative research interviews. A protocol for facilitating interviews will be developed with specific key questions. A sample question is, “Did this community-based exercise intervention support your ability to participate in a regular exercise routine?” Interviews will be recorded, and notes will be taken to assist in identifying main themes.

#### **Procedures at for Day 2 of Initial Assessment (T1D2):**

T1D2 (60 minutes) will be completed at the Center for Applied Research Sciences (CARS) Clinical Research Unit (CRU), which is established within the Institute of Clinical and Translational Sciences. T1D2 will consist of a blood draw (metabolic blood chemistries) and a DXA body scan (body composition). Prior to D2, participants will be instructed to fast the night before (8–10 hours). Trained CARS staff will conduct blood draws and DEXA scans and assist participants, as needed, during T1D2. Research staff may also be present during T1D2 at CARS to assist participants, as needed.

#### ***Body Composition:***

Body composition will be quantified by DXA (General Electric Lunar iDXA) located at the WUSM CRU. DXA is commonly used in research due to its precision and safety. Bone mineral density and whole-body, regional fat, and fat-free (i.e., lean) mass in kg and % will be calculated. Appendicular skeletal muscle mass will be estimated from these data as described and validated by Heymsfield et al.

#### ***Metabolic Blood Chemistries:***

Fasting blood values will be obtained for markers of inflammation (hsCRP), insulin resistance (HOMA-IR using fasting glucose and insulin concentrations), complete blood cell counts (CBC), fasting lipid/lipoproteins (triglycerides, total-, LDL-, HDL-cholesterol), and glycosylated hemoglobin (a marker of glycemic control) at T1 and T2. To explore neurogenesis mechanisms, we will quantify plasma BDNF, IGF-1, and VEGF using ELISA kits (R&D Systems, Minneapolis, MN). Participants will be instructed to fast the night before (8–10 hours). Upon arrival to the CRU after the overnight fast, blood will be collected from the antecubital vein. Blood will be collected with preservatives and stored in [name] laboratory located in [name] on the Washington University School of Medicine Campus. Serum and plasma will be aliquoted into individual vials and frozen (−80° C) until all participants have completed the study intervention.

#### ***F4 Visit 2 etc.***

All participants will complete a 12-week post-assessment within 10 days of completing their final intervention session, either CBEI or EEG. The post-assessment (T2) will also be completed over two separate days with the second day (D2) being completed within

---

10 days of the first assessment day (D1). T2D1 (120 minutes) and T2D2 (60 minutes) will be the same as the initial assessment (T1). In addition, at the T2D1 appointment, participants will complete a 30-minute, semi-structured qualitative interview regarding their experiences while participating in the study. The participants may also be asked to wear a heart rate monitor and accelerometers to measure their intensity levels during testing. T2D1 will take place at the EMC research laboratory, and T2D2 will be completed at the CARS CRU.

## **F5 Visit 3, etc.**

Participants may complete a three-month post-assessment. The post-assessment (T3) will also be completed over one day. T3D1 (90 minutes) will be the same as the initial assessment (T1). The participants may also be asked to wear a heart rate monitor and accelerometers to measure their intensity levels during testing. T3D1 will take place at the EMC research laboratory.

## **F6 Safety and Adverse Events**

### **6.a Safety and Compliance Monitoring**

The research coordinator is the primary scheduler for initial and post-assessments and CBEI exercise sessions; therefore, she will daily monitor assessments and CBEI safety, compliance, and progress. The research coordinator will also be in weekly contact with designated PQHWC staff to update the research team on the safety and compliance of EEG participants.

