to perform a comprehensive variety of strength exercises to promote fat-free mass, muscle endurance, and overall strength. Staff will set up and monitor strength training to ensure that, for each exercise, participants perform at least two to three sets of 10–15 repetitions (reps) at 50%–75% one-rep max (1RM) for each exercise targeting functioning muscle groups. After strength training, participants will complete a 5–10 minute cool-down, and final heart rate, blood pressure, and pain will be assessed. Staff are occupational therapists and physical therapy assistants who have worked in an exercise setting with PwSCI. Staff will be taught the exercise guidelines and exercise session protocols using written materials, demonstration, and practice sessions. Following each exercise intervention session, participants will describe what they liked and did not like, provide a rating (1–5) of how much they gained from the session, and answer an open-ended item requesting suggestions for improvement. At the end of each session, the trainer will rate the participant's perceived participation during the session (1–6) using the Pittsburgh Rehabilitation Participation Scale.

The participants in the EEG will complete an intervention that consists of a one-on-one, hour-long educational session orienting participants to an online resource center, the National Center on Health, Physical Activity, and Disability (NCHPAD). NCHPAD promotes health and well-being for PwD through resources such as adapted exercise videos, information on accessible fitness equipment, personalized exercise videos tailored to PwD, and an individualized 14-week exercise program. Participants will be given an overview of NCHPAD and asked to identify resources of interest on the website. Each participant will be asked to use resources on NCHPAD to engage in physical activity for 12 weeks. Each participant will receive a weekly phone call to inquire about their physical activity, exercises engaged in, RPE during exercise, and whether any resources were used.

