## **2.e Risks and Benefits**

### **Risks:**

A likely or common mild risk that may occur from participating in the testing sessions and/or participating in any exercise program for 12 weeks is that participants may experience muscle soreness or fatigue. Participants will have planned rest breaks, be allotted any unplanned rest breaks requested, and be encouraged to maintain hydration levels during exercise training. There is also a mild risk of emotional distress or discomfort in completing the questionnaires. Participants will complete questionnaires in

---

a private area and will be allowed to decline to answer any of the questions that make them uncomfortable.

An uncommon risk that may occur is an exercise-related injury, such as muscle strain or sprain. To help ensure that participants are safe to exercise, they will be required to have a physician's referral to participate in this study; in addition, a heart rate monitor and accelerometers will be worn during selected testing and exercise sessions (if assigned to the CBEI) to ensure accurate monitoring of their health status. They will also be educated about the proper and safe way to exercise before the study begins. For CBEI participants, trained research members will be present during all sessions to ensure participant safety. Proper precautions to avoid injury, including stretching and rest breaks, will be employed to reduce the risk of soft tissue damage.

Another risk to participants includes potentially dangerous conditions associated with SCI, such as autonomic dysreflexia, during assessments and exercise training. However, this is a very small risk. All research team members are familiar with serious conditions, such as autonomic dysreflexia, and medical precautions to monitor any life-threatening conditions will be taken during testing and training. In the highly unlikely event a participant experiences a medical emergency, immediate appropriate actions will be taken by research staff.

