**2.g When and How to Withdraw Subjects**

The research coordinator of the study is primarily responsible for scheduling testing and exercise sessions for participants. The research coordinator will also be in weekly contact with designated PQHWC staff to update the research team on the attendance/compliance of CBEI participants. If deemed that a participant is non-compliant with the exercise program protocol, the research coordinator will contact the participant and inform him/her of the withdraw policy. If the participant remains non-compliant over the following two weeks, he/she will be withdrawn by the research team and will be contacted via phone.

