#### *Medical Monitoring:*

There will be a physician who will provide medical monitoring of the body composition and metabolic blood chemistry appointments.

i        **Investigator only**

ii        **Independent expert to monitor**

Not applicable

iii        **Institutional Data and Safety Monitoring Board**

To ensure that participants are medically stable and safe to participate in the project, physician's approval and a signed release will be required prior to the initial assessment. During assessment and exercise sessions, participants will be monitored for safety, pain, and any signs of distress. Heart rate monitors will be worn during the VO2 testing. Blood pressure will be taken at the beginning of all testing and intervention sessions. If a participant reports an 8/10 pain level prior to a session, the session will be canceled and rescheduled. If at the end of a session the participant reports pain 8/10 or higher, the rating will be documented in the study's adverse event tracking log. Participants may be dismissed from participation if they rate pain 8/10 or higher over three consecutive sessions. Trained research investigators will be present during all sessions to ensure participant safety. If a participant is uncomfortable with having their blood drawn for metabolic testing, they may choose to skip that portion and still continue within the study. All members of the research team are familiar with potentially dangerous conditions associated with SCI, such as autonomic dysreflexia, and will take appropriate actions if a

---

participant experiences a medical emergency. Adverse events will be reported to the IRB consistent with the IRB's reporting guidelines. We will take every precaution to ensure participant safety while avoiding risks.

**Safeguarding of data:** Researchers will assign participants a code to de-identify all data according to HIPAA policies. Data will be stored in a password-protected computer to guarantee participant privacy. To ensure quality of data collection, a research member will oversee each piece of equipment (i.e., Metabolic cart, heart rate monitor, and accelerometers) for immediate detection of technological malfunctions during sessions.

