### **G2 Interim Monitoring and Early Stopping**

The research coordinator is the primary scheduler for initial and post-assessments and CBEI sessions; therefore, she will daily monitor assessments and CBEI safety, compliance, and progress/stopping. The research coordinator will also be in weekly contact with designated PQHWC staff to update the research team on the safety and compliance of CBEI participants. Designated PQHWC staff will be present to supervise all CBEI participants to monitor safety.

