## ***I2 Auditing and Inspecting***

Ongoing monitoring will also be conducted to ensure fidelity. All interventionists have worked with people with SCI, understand the implications of SCI, and have extensive knowledge about wheelchairs. [name] will train all interventionists on the CBEI and EEG protocols. Interventionists will be asked to complete a practice session. To ensure standardization of the intervention delivery and to reduce drift, [name] will monitor the fidelity of the training sessions by completing a fidelity monitoring checklist on 20% of the CBEI and EEG participants during one of the sessions. The monitoring checklist will include aspects of the session and instructions given by the interventionist. The research coordinator will review all participant (CBEI and EEG) files weekly to ensure that the interventionists are completing all paperwork and documenting intervention sessions.

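### Planned adverse-event capture during the 12 weeks differs by arm, and the EEG safety route and the adverse-event definition need reconciling

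*Combined protocol and SAP*

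**What the plan says.** **CBEI arm.** Section E1 schedules 36 staff-led sessions, three a week for 12 weeks. Vitals and pain are taken at the start, and at the end "final heart rate, blood pressure, and pain will be assessed". Section E2 2.e adds: "For CBEI participants, trained research members will be present during all sessions to ensure participant safety". Under Medical Monitoring in F6 6.a, if "at the end of a session the participant reports pain 8/10 or higher, the rating will be documented" in the adverse event log.

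**EEG arm.** Section E1 gives one education session of an hour, then 12 weeks of self-directed activity with a "weekly phone call to inquire about their physical activity, exercises engaged in, RPE during exercise, and whether any resources were used".

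**Safety route.** Section F6 6.a has the coordinator follow CBEI daily and be in "weekly contact with designated PQHWC staff to update the research team on the safety and compliance of EEG participants". Section E2 2.g instead refers to "weekly contact with designated PQHWC staff to update the research team on the attendance/compliance of CBEI participants", and G2 to "weekly contact with designated PQHWC staff to update the research team on the safety and compliance of CBEI participants".

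**Definition.** Section F6 6.b defines an adverse event as an injury or medical event caused by the assessments or the exercise training program. Section 6.c, under Severity, counts any event that needs medical care and sets no causal condition. The Relationship heading in 6.c has no text under it.

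**Use.** Section 6.d says that adverse events will be logged and reported in publications.

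**The concern.** A published adverse-event count reflects both what happened and how hard anyone looked. Here one arm is watched in person, with a rule that writes certain pain ratings into the log. The other arm is telephoned about its activity. If readers compare counts by arm, the closer observation of CBEI could pass for greater harm. That matters for a pilot whose stated use is to plan a larger trial.

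Two wording problems add to this. It is unclear through whom EEG safety information reaches the research team. It is also unclear whether an injury during EEG self-directed exercise meets the definition at all, because 6.b does not say whether that exercise belongs to the training program it names.

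**Working it through.** **1. The plan's own figure.** 3 sessions per week x 12 weeks = 36 CBEI sessions per participant, which matches E1. It is a scheduled maximum.

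**2. Checks that can trigger a log entry during the 12 weeks.** The rule in F6 6.a applies to pain at the end of a session. A high rating before a session leads to rescheduling and is not stated to be logged, so there is one check per session.
- CBEI: 36 x 1 = 36 per participant.
- EEG: 0 per participant, or 1 if the education session counts as a session and pain is asked there.

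These are scheduled checks, not events. Assessment days, if they count as sessions, add the same number to each arm (two days at T2 and one at an optional T3) and leave the difference unchanged. T1 precedes randomisation.

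**3. What the EEG call covers.** Four topics are listed: physical activity, exercises done, perceived exertion and use of resources. None concerns injury, symptoms or medical care. No scripted adverse-event question is documented for CBEI either; what CBEI has in addition is direct observation and the log rule.

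**4. What both arms share.**

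| Source | Section | Why it does not close the gap |
|---|---|---|
| Monitoring on assessment days | F6 6.a | Not during the 12 weeks |
| CORE health items and PROMIS at T1, and again at T2 and T3 | F3, F4, F5 | Health status and symptoms, with no stated link to the log |
| T2 interview | F4 | Covers experiences of the study |
| Withdrawal for a medical complication | E2 2.f | Assumes the event is known and names no route |
| Weekly file review | I2 | Checks paperwork and session documentation |

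**5. The safety route, read both ways.**
- If EEG in 6.a is a slip for CBEI, 6.a names no EEG route.
- If it is intended, the route is incomplete. J1 places the gym (PQHWC) staff at CBEI sessions, J4 gives EEG participants gym membership only after the 12 weeks, and no section says who makes the EEG calls.

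**6. The definitions, applied to the same event.**

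| Event | 6.b | 6.c |
|---|---|---|
| Strain from a CBEI session, no medical care | Meets | Does not meet |
| Unrelated illness needing medical care | Does not meet | Meets |
| Strain from EEG self-directed exercise, no medical care | Unclear | Does not meet |

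An end-of-session pain rating of 8/10 is logged under 6.a although it need not meet either definition.

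**The case against.** The strongest reply is that EEG participants are not invisible. CORE and PROMIS are repeated in both arms, everyone who reaches T2 is interviewed, assessment days are monitored, and the coordinator "will review all participant (CBEI and EEG) files weekly to ensure that the interventionists are completing all paperwork". The medical-complication rule in E2 2.f covers both arms and presupposes that EEG events become known. Nothing stops a participant from volunteering an injury on a call. All of this stands and narrows the gap, so a reader who inferred that EEG has no safety capture would go too far. What remains is that none of these is a stated adverse-event enquiry during the intervention.

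A reader might also infer that 6.a is plainly wrong. The text does not establish that. Its two sentences can be read as a scheme for both arms, CBEI daily and EEG weekly, and weekly contact could cover both. I2 has interventionists trained on both protocols and documenting sessions in both arms' files, so staff might know of EEG events. The near-identical sentence in G2 makes a slip possible, and the three sections still have to be reconciled.

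Supervised arms are always watched more closely, and that cannot be designed away. The question asked and the definition applied can be made the same.

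Finally, 6.b and 6.c apply to both arms, so apart from the coverage of EEG exercise their conflict is a separate fault and not a source of differential capture. The sentence in 6.c may also be a misplaced severity rule. Both remarks are fair, and neither removes the need for one definition.

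**Conclusion.** The point holds as a difference in planned capture together with two wording conflicts. Its only firm size is 36 scheduled log-trigger checks per CBEI participant against 0 (or 1) per EEG participant over the 12 weeks, assuming full attendance and reading the trigger as an end-of-session rule.

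Two stronger conclusions are tempting. The first is a numerical bias, from a ratio of contacts or an assumed rate of high pain ratings. The documents do not support one: both arms are contacted every week, any ratio depends on which contacts are counted and on attendance in each arm, and no event rates are given. Equal pain probabilities after supervised exercise and after an education session would be pure assumption. The second is that the trial's main result is compromised. It is not: G4 plans no between-arm test of harms, and the VO2peak comparison does not use the log.

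The consequence is also conditional, since 6.d does not say that events will be shown by arm. If they are shown or read that way, the likely direction is to make CBEI look relatively more harmful. The correction is worth making because it is cheap.

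**What to change.** 1. Reconcile E2 2.g, F6 6.a and G2, and name for EEG who collects safety information, from whom and how often.
2. Ask one identical scripted question weekly in both arms, on the existing EEG call and at one CBEI session per week. For example: *Since we last asked, have you had any injury, new or worse symptom, or medical care?* If it is also asked at T2 or T3, use a self-completed form or someone other than the assessor, whom E2 2.d keeps blinded, because answers could reveal allocation.
3. Reconcile 6.b and 6.c into one definition applied to both arms. It should state whether EEG self-directed exercise is covered, with relatedness and severity classified separately.
4. In publications, take by-arm counts from the scripted question. List separately every event found only by session observation, both pain-trigger entries and other staff-observed events such as autonomic dysreflexia, so that none is dropped.

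**Cost.** Protocol wording plus 20 participants x 12 weeks = 240 asks per arm at most, or 480 in total. Asking at T2 and T3 as well adds at most 20 x 2 = 40 per arm, giving 280. Withdrawals lower these figures, since E2 2.h gives withdrawn participants no follow-up assessment. No visits are added. There will be more events to log and classify, and a difference between telephone and face-to-face asking will remain.
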